Many naturally-occurring compounds in dietary plants and animal products possess a variety of physiological functions which promote human health and wellbeing, and contribute to better diet-related-disease (DRD) prevention and particularly the Metabolic Syndrome (MS). These compounds, known collectively as bioactives (natural components of foods that possess biological activity in addition to their nutritional value), normally occur at very low concentrations in foods, and their effects on human health are being studied intensively for their possible contribution toward reducing the risk of many DRDs. Identifying bioactives, establishing their mechanisms of actions and health effects are all active areas of scientific inquiry and, through industrial exploitation, potential societal benefit.

Scientific understanding of the role and mechanisms of bioactives is fragmented. Research often addresses the theoretical possibility of health improvement effects rather than their real, practical use for everyday diets. Bioactives cannot be considered as discrete chemical compounds and research must focus on bioactive-enriched foods (BEF), if consumer demands for foods delivering appropriate health and wellbeing benefits are to be fulfilled. The general objective of PATHWAY-27, a pan-European interdisciplinary team of 16 life/social scientists and 10 high tech/ food processing SMEs, addresses the exploitation of bioactive compounds as ingredients of foods that, within the common diet, could significantly benefit human health and wellbeing. PATHWAY-27 will evaluate the effectiveness of docosahexaenoic acid (DHA) alone or in combination with two other bioactives, beta-glucan (BG) and anthocyanins (AC), chosen for known/claimed effectiveness in reducing some risk factors of MS. These compounds will be considered as ingredients of BEFs enriching three different widely consumed food matrices (dairy-, bakery-, egg products) and not pure compounds. This will allow us a better understanding of possible synergisms and bioactive matrix interactions.

BEFs to be tested in PATHWAY-27 clinical studies will be designed and selected in preceding work packages of this European FP7 project. SMEs will be deeply involved in the elaboration of BEFs. The purpose of pilot clinical studies will be to select, for each of the three food matrices, the BEF delivering the greatest reduction in serum triglycerides (TG) or increase in HDL-cholesterol (HDL-C). Three pilot studies will be conducted in three clinical research centres (Max Rubner Institute, Karlsruhe, Germany; University of Leeds, United Kingdom; and Human Nutrition Research Centre of Auvergne, France), each participating centre focusing on a specific food matrix. Each pilot study will be randomized and double blind and aim to identify the most active BEF within a specific food matrix. The BEFs selected after pilot studies will then be tested in the subsequent, larger interventional study, on their ability to modulate a wider range of metabolic outcomes.

2. Aim

The aim of this multi-centre, randomized, double blind, parallel pilot dietary intervention study is to identify the BEF achieving the greatest effect on lipid parameters. Three different matrices, dairy-, bakery-, and egg products, containing DHA, BG and AC given alone or DHA associated with BG or AC will be tested. Thus, 15 products, five in each centre will be tested.

3. Study population

3.1 Population

Three hundred participants will be included. Men and women aged 18 to 80 yrs, at risk for metabolic syndrome, will be eligible.

3.2 *Sample size calculation*

In each pilot intervention, 100 participants will be divided in 5 subgroups of 20 participants, each receiving a BEF within a specific food matrix (dairy-, bakery-, egg products) enriched with DHA, BG or AC alone, or DHA+BG, or DHA+AC. In this exploratory study, within each matrix, 20 subjects per arm would be sufficient to obtain measurable changes for the parameters that will be tested.

3.3 *Inclusion criteria*

MS is defined when three of the following criteria are met:

- elevated waist circumference (men \geq 102 cm; women \geq 88 cm)
- elevated fasting triglycerides (\geq 150 mg/dL)
- reduced fasting HDL-cholesterol (men \leq 40 mg/dL; women \leq 50 mg/dL)
- elevated blood pressure (systolic \geq 130 mmHg and/or diastolic \geq 85 mmHg) or hypotensive treatment
- elevated fasting glucose (\geq 110 mg/dL)

Subjects will be eligible to the pilot study if they present with two to four of the MS criteria, at least one of them being alteration of fasting triglycerides or HDL-C cholesterol.

3.4 *Exclusion criteria*

Participants are excluded if three or more clinical criteria for metabolic syndrome are met. Additionally, major exclusion criteria are:

- regular drug therapy with impact on serum lipids;
- diabetes (fasting glucose $>$ 1.26 g/L, or anti-diabetic treatment);
- recent history of cancer or cancer treatment (less than 2 years);
- active or recently diagnosed intestinal malabsorption or disorders associated with malabsorption: Crohn's disease, short bowel syndrome, Pancreatic insufficiency, cystic fibrosis, Tropical Sprue, whipple's disease, chronic pancreatitis, gastrojejunostomy, surgical treatments for obesity, cholestasis, biliary atresia, parasite infections, HIV/AIDS
- familial dyslipidemia;
- use of medication known to cause malabsorption: tetracycline, cholestyramine, thiazide diuretics, aluminium/magnesium hydroxide, cochlincine, neomycin, methotrexate, methyl dopa, and allopurinol, and laxatives
- illegal drug use, chronic alcoholism or active smoking;
- consumption of nutritional supplements containing DHA, BG or AC;
- history of allergy or intolerance to any components used in BEFs, celiac disease, lactose intolerance, allergy to milk or egg proteins;
- institutionalised patients, those who lack autonomy to consent or are unable to meet all examinations;
- women who are pregnant, lactating or actively trying to conceive;
- participation in other clinical trials that may impact on outcome;
- subjects deprived of their liberty by judicial or administrative decision.

3.5 *Recruitment*

Possible participants will be identified from databases of interested volunteers. Those who meet eligibility criteria will be invited to participate. Additionally, recruitment will include interviews in local radio stations and advertisement in local newspapers if necessary. Waist circumference and history of hypertension, dyslipidemia and hyperglycemia will be included into the advertisement to be shared by the three centres. Interested persons will be contacted by

phone/email to answer an eligibility questionnaire to be shared by the three centres. Eligible persons will be invited for baseline examinations. Written consent will be obtained before any examination takes place.

3.6 *Subject withdrawal criteria*

[figure not shown]
Subjects may discontinue their participation in the study at any time. A subject may be withdrawn from the study for any of the following reasons:

- withdrawal of consent - any subject may withdraw from the study at any time
- significant deviation from the protocol
- lost of follow-up
- death
- incidental illness or condition interfering with protocol
- occurrence of a serious adverse event or significant alteration in clinical and/or laboratory parameters. In these cases, appropriate actions will be taken. The sponsor will be notified immediately.

4. **Study design**

This is a multi-centre, randomized, double blind, parallel pilot dietary intervention study without a placebo. In total, 300 men and women at risk for metabolic syndrome will be recruited. Each of the three participating study centres (MRI, ULE, CRNH) will recruit 100 volunteers. Participants will be divided in five groups of 20 each receiving BEF enriched with DHA, BG, or AC alone or DHA+BG, or DHA+AC based on bakery, dairy or egg. In each pilot, BEF belonging to a specific food matrix will be studied (Figure 1). Participants will be required to consume the allocated BEF daily for a period of four weeks. At baseline and after 4 weeks of intervention, fasting blood samples will be collected for further analysis. Additionally, blood pressure and anthropometric data will be collected.

Figure 1 Scheme of pilot studies

5. Intervention

5.1 BEF delivery

Bakery, dairy or egg product-based BEFs will be produced by SMEs involved in the project, according to the protocols and formulations established in other work packages of the PATHWAY-27 program. BEF will be stored and supplied to participant centres according to shipment and storage rules given by producers. For each matrix, five different BEFs will be prepared and enriched with DHA, BG, or AC alone or DHA+BG, or DHA+AC. The putative amounts of supplied bioactives are given in table 1, and will be the same regardless of the food matrix.

Table 1 Putative bioactive supplies

[figure not shown]
Bioactive	Docosahexaenoic acid (DHA)	Beta-glucan (BG)	Anthocyanins (AC)
Daily supply	250 mg	3 g	320 mg

Participants will be advised to consume their product daily. No placebo or control product will be given. The BEF will be consumed in replacement of similar foods, and not in addition to the usual diet.

5.2 Study protocol (Figure 2)

Recruitment will be performed until day -7. Eligible participants will be included and randomly allocated to one of the five groups. On days 1 and 28 after inclusion, each participant will come in to the laboratories for clinical and biochemical investigations.

Figure 2 Study protocol

Participants are advised to consume the tested products daily in replacement of the similar “common” food they consume normally, by including them in their regular meals. Besides BEF consumption, participants will be on a free diet, however a list of foods to be consumed no more than once per day will be provided to each participant. Dietary supplements containing DHA, BG or AC must not be taken.

5.3 Outcome assessment

Primary outcome: fasting serum TG and HDL-cholesterol will be measured at baseline and at the end of the study by standardized enzymatic methods.

Secondary outcomes (days 1 and 28):

- blood pressure
- body height and weight, BMI
- abdominal circumference
- blood glucose

At the beginning of the study participants will be asked to complete a food frequency questionnaire specific to the foods described on the restriction list. The purpose of this is to collect information about exposure to the bioactive ingredients from natural sources and highlight high/low level consumption that could be a potential confounding factor.

Participants at Leeds will also complete a 24 hour dietary recall at the baseline and end visit to collect information about energy, nutrient and alcohol intake. The purpose of this exercise is two-fold. Firstly to look for potential confounding factors, and secondly to investigate whether this type of dietary assessment tool is appropriate to capture the information required to perform an effective dietary assessment.

At the baseline and final visit participants will provide information about abdominal symptoms that they experience. This has been designed to assess whether the BEF have an impact on appetite and intestinal behaviour.

Participant acceptability of the BEF will be assessed at days 1 and 28 of the intervention using a food preferences questionnaire to collect data.

5.4 Safety assessment

- An adverse event (AE) is any untoward medical occurrence in a subject consuming a study product and which does not necessarily have a causal relationship with the study product.
- A serious adverse event (SAE) is any untoward medical occurrence that at any dose: results in death; is life-threatening (at the time of the event); requires inpatient hospitalisation or prolongation of existing hospitalisation; results in persistent or significant disability or incapacity. In the present study, expected adverse events may be linked to venous punctures for blood samples and digestive discomfort associated with BEF consumption. No serious adverse event is expected.

5.4.1 Declaration of AE/SAE

Any AE/SAE will be notified to the principal investigator who will ask for medical advice if necessary. The study coordinator will be informed of any SAE. In addition, AE/SAE will be reported in the Electronic Data Capture (EDC) System. Anybody who has access to the EDC System will have to report AE by selecting the patient and completing the AE/SAE form (annex 9). The investigators will then receive email notification of the AE/SAE which will be handled according to the seriousness of the event: in case of SAE a report will be sent within 24 hours to the sponsor; monthly reports will be created about non-serious events.

To detect possible non-reported AE, checks will be inserted into eCRF forms (e.g. alert and redirect the physician to the AE/SAE form if he/she enters an abnormal finding). The monitors will also have to raise data clarification queries if they encounter suspicious data. In the latter case the principal investigator will have to confirm the data and to complete an AE/SAE report or corrects the data.

Participants will be informed to contact the person responsible for their inclusion in the study (principal investigator) in case of any unexpected health event. On day 28, the clinical examination will look for any adverse effect, and if necessary, complementary investigations will be performed.

5.5 Methods of measurement

Blood pressure will be measured in participants after being at rest for five minutes in seated position followed by two additional measurements separated by two minutes each. A calibrated sphygmomanometer (e.g. *Boso-Carat professional*) will be used for the pilot study and appropriate sized cuffs are applied after measurement of arm circumference.

Body weight will be measured using a calibrated balance with the participants barefoot and dressed in underwear.

Height will be determined using a calibrated stadiometer.

Waist circumference will be measured in standing position between the iliac crest and the lowest rib using a measuring tape (WHO guideline).

All measurements will be performed by trained study nurses strictly adhering to SOPs.

Serum markers (serum TG, HDL, fasting glucose) will be determined by standardized enzymatic methods.

5.6 *Harmonization of methodologies and standard operating procedures (SOPs).*

The SOPs to be applied by the three centres are given in the following annexes.

1. SOP Recruitment of participants for clinical trials
2. Information for participants
3. Consent form
4. SOP Collection of blood by venepuncture from fasted subjects and preparation of serum
5. SOP Quantification of HDL-cholesterol in serum samples
6. SOP Quantification of triglycerides in serum samples
7. SOP Quantification of glucose in blood samples
8. SOP Physical examination
9. Adverse event/serious adverse event declaration
10. Composition of pancakes
11. Risk assessment
12. Pancake consumption record
13. Clinical Research File – Screening – Visit 1
14. Clinical Research File – Baseline – Visit 2
15. Clinical Research File – Endpoint – Visit 3
16. Recruitment advert
17. Recruitment email
18. Telephone screening questionnaire
19. Letter to participant GP
20. Restricted food list
21. Abdominal symptoms questionnaire
22. Study instructions for participants
23. Food preferences questionnaire
24. 24 hour dietary recall
25. Visit 1 Invitation letter
26. Visit 2 invitation letter
27. Food frequency questionnaire – restricted foods
28. References

5.7 *Extraction, processing, and storage of biological samples*

Blood will be sampled after an overnight fast (10 to 14 hours). Serum will be obtained by centrifugation at 4°C 20 min 1800g, immediately shipped to the accredited analysing lab or aliquoted and stored at -80°C until further analysis. Cellular fractions will be discarded and destroyed by incineration. Triglycerides, HDL-cholesterol and glucose will be measured by internationally validated standard enzymatic assays. The analysing lab is responsible for proper disposal of the biological material according to local rules. Biological materials will be kept until the publication of the study in order to be able to perform eventual control measurements. Thereafter, the analysing lab is responsible for proper disposal of the biological material according to local rules.

5.8 *Compliance assessment*

Compliance will be assessed after collection of all food packages on day 28 and using a record that participants are asked to complete during the trial.

6. Statistical considerations

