 - Disinfect the phlebotomy site by swabbing the skin in small outward circles with an alcohol swab. Do not touch the prepared puncture site with your fingers after disinfecting the skin.
 - Using aseptic technique, insert the needle of the vacutainer/sarstedt device into the vein. If possible, always allow the full amount of blood to be drawn by each evacuated tube when using the vacutainer/sarstedt system tubes.
 - After drawing, carefully mix the blood in tubes containing additives by inverting the tubes several times. After serum preparation, place the tubes in suitable bags, and if possible store at 2-8 °C until further use.
 - After drawing the required blood samples, release the tourniquet. Remove the needle from the vein, cover the puncture site with a cotton swab, and hold until adequate haemostasis is visible.

- After completion, needles must be properly disposed of in a puncture resistant container to be destroyed by incineration. Any other non-sharp material that has been in contact with blood fluids must be disposed by incineration in a suitable holding bag.

Discontinuation of the procedure during blood collection

- The procedure may be stopped if:
- The subject becomes distressed. In which case remove the needle only when it is safe to do so.
- There is any breach of protocol or event that compromises the safety of the subject or the phlebotomist. Inform the clinical researcher immediately.

Labelling

Appropriate labelling of the tubes is essential for appropriate handling and analysis of the samples, ensuring that samples are not wasted unnecessarily.

Each tube must be clearly labelled with:

- Date of collection
- Time of collection
- Subject's code
- Type of analyses to be performed or barcode that includes these informations according to operating lab.

In LIGHT, tubes must be placed inside polyethylene bags, sealed and labelled.

Preparation of serum

Some analyses require the use of serum. Serum will be prepared according to the following procedure:

1. Blood samples will be allowed to clot for 30 minutes at room temperature in the collection tubes (no heparin).
2. Centrifuge the tubes for 10 min at 820 RCF at 4°C.
3. Collect the supernatants in suitable new, sterile and tubes labelled as described above.
4. Store at -80°C if storage is required.
5. Discard old tubes with blood cells and remnants in a clinical waste bag and destroy by incineration.

Reporting

Any accident or mishap will be reported to the principal investigator.

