- Every time that the equipment is switched off
- Every time that the equipment is cleaned or maintained
- Every time that any trouble shooting procedures have been undertaken
- Every time that any of the reagents or optical components are changed
- Each instrument brand/model will have a maximum calibration stability that should be complied to. Calibration standards will be applied according to manufacturer Instructions. A log of calibrations should be kept including the date, the lot number of the reagents used, the date the reagents were first opened and their expiry date.

Quality control

Appropriate control tests should be routinely performed using control samples (upper and lower limit controls). Each laboratory may have its own quality control procedures, but as a minimum, these control tests should be performed:

- Twice daily
- After each calibration
- If there are any issues with analyses that suspect deviations from the normal range of analysis
- Quality control standards should be purchased and used according to the manufacturer's instructions. A log of quality control tests should be kept including the date, the lot number of reagents used, the date the reagents were first opened, and their expiry date.

Samples

Blood will be used for analysis.

- Blood should be collected, prepared and stored according to SOP.
- Before analysis, the operator should check that check the tubes for signs of leakage or contamination, and should check that the labelling is correct for the type of test requested. The operator shall keep a record of the samples analysed by subject's code.
- Minimum volumes drawn will be in accordance with manufacturer instructions.
- Unconjugated and conjugated bilirubin, lipids and ascorbic acid are some of the interfering substances (>10% interference).
- For details of how the serum should be handled and loaded onto the machine, please adhere to manufacturer's instructions.

Range of analysis:

For blood samples, the method is linear for the following range:

to 750 mg/dL (0.3 to 41.6 mmol/L)

Conversion factor: mg/dL x 0.0555 = mmol/L

Precision:

Each instrument will have specific performance ranges, but generally the percentage coefficient of variation (%CV) should be below 3%. Replicate analyses should be performed for each sample.

Expected values:

Normal range: 74–106 mg/dL (4.1–5.9 mmol/L)

High fasting: ≥ 110 mg/dL (> 6.1 mmol/L)

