- Stand to the right, behind the subject and locate the top of the right ileum with the fingers.
- Stand to the right of the subject and located the bottom of the lowest rib.
- Place the measuring tape between the top of the right ileum and the bottom of the lowest rib.
- Ensure that the measuring tape is horizontal to the floor all around the subject.
- Hold the zero value on the tape below the measurement value, without compressing the skin.
- At the end of a normal expiration, take the measurement and record on the CRF to nearest 0.1 cm.

Measurement of blood pressure:

- Switch the blood pressure monitor on.
- Instruct the subject to lie down on the medical bed, or to sit down with the right arm rested on the arm rest at heart level.
- Instruct the subject not to talk during the entire procedure.
- Select appropriate sized cuff according to arm circumference.
- Connect the cuff to the monitor.
- Place the cuff around the arm around 2 cm from the inner side of the elbow joint, with the artery position mark aligned with the brachial artery.
- Wrap the cuff snugly around the arm and secure with the Velcro fastening.
- Instruct the subject to relax their arm and open their hand with palm facing upwards.
- Press the on button and wait until the measurement is given. Record both diastolic and systolic pressure to the nearest 0.1 mmHg on the CRF.
- If you need to stop the measurement at any point, press the STOP button to deflate the cuff instantly.

At the end of the examination:

- a. Ensure that you are satisfied with the quality and accuracy of all measurements recorded. If not, then repeat as necessary.
- b. Instruct the subject to get dressed.
- c. Thank them for their participation.

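### Sections 5.5 and 5.7 conflict with SOPs 9.8 and 9.4 on how blood pressure is taken and serum is spun, so centres or visits may use different procedures

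*Protocol*

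**What the plan says.** **Blood pressure.** Section 5.5 has it taken "after being at rest for five minutes in seated position followed by two additional measurements separated by two minutes each". SOP 9.8 says "Instruct the subject to lie down on the medical bed, or to sit down", then "Press the on button and wait until the measurement is given", and has that result recorded. It gives no rest period and no repeat readings, except that staff may repeat any measurement whose quality does not satisfy them. It places blood pressure last, after weight, height and waist. The forms for visits 1, 2 and 3 (annexes 9.11 to 9.13) each have one line for systolic and one for diastolic pressure.

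**Serum.** Section 5.7: "Serum will be obtained by centrifugation at 4°C 20 min 1800g". SOP 9.4, after 30 minutes of clotting at room temperature: "Centrifuge the tubes for 10 min at 820 RCF at 4°C".

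**Glucose.** Section 5.5: "Serum markers (serum TG, HDL, fasting glucose) will be determined by standardized enzymatic methods". SOP 9.7: "Blood will be used for analysis", although the same SOP later refers to handling serum.

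**Status of the SOPs.** Section 5.5 has nurses adhere strictly to the SOPs for all measurements. Section 5.6, on harmonisation, applies the SOPs to all three centres. Nothing says which text prevails where the body and an SOP differ.

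**The concern.** Blood pressure is used twice: as one of the metabolic syndrome criteria counted for eligibility (130/85 mmHg, section 3.3) and as a secondary outcome on days 1 and 28 (section 5.3). Posture, rest and number of readings can all affect the recorded value. As written, SOP 9.8 would let a participant lie down on day 1 and sit on day 28, and that difference would enter the change score as error. At screening, one criterion can decide eligibility: section 3.3 requires at least two, and section 3.4 excludes anyone with three or more.

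The spin settings concern the serum for fasting triglycerides and HDL-cholesterol, the primary outcomes. The analyte SOPs (9.5 to 9.7) argue that change scores are unaffected by the lack of analyser harmonisation. That argument is about analysers. It does not cover how the specimen is prepared or how blood pressure is taken.

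**Working it through.** The plan gives no figure to reproduce here. The check is a comparison of texts plus two small calculations.

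**1. Blood pressure, item by item**

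| Item | Section 5.5 | SOP 9.8 and forms | Relation |
|---|---|---|---|
| Posture | Seated | Lying or seated | Direct conflict |
| Rest | 5 min | Not mentioned; follows other examinations | Omission |
| Readings | 1 + 2 = 3, two minutes apart | One described | Omission |
| Recorded value | Not stated | One systolic and one diastolic field | Not defined |

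**2. Serum**

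| Item | Section 5.7 | SOP 9.4 |
|---|---|---|
| Clotting | Not stated | 30 min, room temperature |
| Force | 1800 g | 820 g (RCF is a multiple of g) |
| Time | 20 min | 10 min |
| Temperature | 4°C | 4°C |

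Force × time: 1800 × 20 = 36,000 g·min against 820 × 10 = 8,200 g·min. The ratio is 36,000 / 8,200 = 4.39. No operator can follow both. The ratio shows only that these are different procedures. It is not an effect on any analyte.

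**3. What the number of readings can do at the 130 mmHg threshold**

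Assumptions, none from the documents: true rested systolic pressure 127 mmHg; normal, independent reading errors with within-visit SD s of 4 to 8 mmHg; the three readings of 5.5 averaged.

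- One reading: P = 1 − Φ((130 − 127)/s).
- Mean of three: P = 1 − Φ((130 − 127)/(s/√3)).
- One reading running 5 mmHg high for lack of rest: P = 1 − Φ((130 − 127 − 5)/s).

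| s (mmHg) | One reading | Mean of three | One reading, +5 mmHg |
|---|---|---|---|
| 4 | 0.227 | 0.097 | 0.691 |
| 6 | 0.309 | 0.193 | 0.631 |
| 8 | 0.354 | 0.258 | 0.599 |

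For a person just below the threshold, the procedure changes the chance of being counted as meeting the criterion. This applies only to people not on hypotensive treatment, because treatment meets the criterion whatever the reading.

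**4. Precision of the blood pressure value**

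With independent errors, the mean of m readings has 1/m of the within-visit error variance of one reading. That is a reduction of 1 − 1/3 = 67% for three readings. Positive correlation between readings makes the reduction smaller, so 67% is an upper bound. It concerns within-visit error only, not the whole variance of a 28-day change.

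**5. Where a procedural difference would show**

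Each centre tests one matrix and randomises to five arms from its own list (sections 1 and 6.1). A procedure applied consistently within a centre acts on all five arms alike and largely cancels in within-matrix comparisons of change. What remains exposed is a switch between day 1 and day 28, the comparability of the populations admitted at the three centres, and the food-matrix effect in the section 6.4 model. That last effect is already inseparable from centre by design.

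**The case against.** **Silence is not contradiction.** SOP 9.8 neither forbids a rest nor limits staff to one reading, so a nurse can carry out all of 5.5 without breaching it. This stands in part: only posture is a direct conflict in the blood pressure text. But an SOP that must be followed strictly and leaves out two steps the protocol requires does not secure those steps, and a form with one field does not preserve three readings.

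**The forms may be local, and a single field may hold a summary value.** The visit 2 form names the Leeds site, and a rule for combining readings is often left to the statistical analysis plan. This is fair. The absence of the rule is therefore not a fault in itself; the mismatch between 5.5, the SOP and the forms is.

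**Glucose is loose wording.** SOP 9.7 speaks of both blood and serum, the only preparation SOP yields serum, and section 6.4 calls a serum endpoint blood TG. This stands. A reader might infer that two specimen types are in use and that values shift at the glucose cut-offs. The documents do not support that; it is a terminology correction.

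**Divergence is not shown.** A reader might infer that the centres do measure differently. The documents only permit it, and the natural reading of 5.6 is that all three use the same SOPs.

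**The spin ratio proves nothing about lipids.** Correct. A reader might take the 4.4-fold ratio as a distortion of the primary outcome, but nothing in the documents links either setting to triglyceride or HDL-cholesterol values.

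**The pilot's main comparison is protected.** This largely stands where each centre is consistent. Because the arms are blinded, haphazard switching between visits would be expected to add noise rather than favour an arm.

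**Conclusion.** The point holds as a conflict in the current text that should be reconciled. Posture and centrifugation are direct contradictions. The rest period and the repeat readings are required in 5.5 and missing from SOP 9.8 and the forms. Because 5.5 and 5.6 put both versions in force, centres or visits may use different procedures.

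The foreseeable cost is extra error in blood pressure change and misclassification near 130/85 mmHg. Under the assumptions above, the chance that someone at 127 mmHg is counted as meeting the systolic criterion is 0.23 to 0.35 with one reading and 0.10 to 0.26 with a mean of three. It would be 0.60 to 0.69 if a single unrested reading also ran 5 mmHg high. These figures illustrate sensitivity and do not estimate what happened in the trial.

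For triglycerides and HDL-cholesterol the documents give no basis for sizing an effect, and none is claimed. Nor do the documents support a conclusion that the choice of product within a matrix is biased.

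**What to change.** - Rewrite the blood pressure part of SOP 9.8 to match section 5.5: one posture, the rest period, and three readings at the stated interval.
- Give the visit forms fields for all three systolic and diastolic readings, and state in the protocol or analysis plan how the analysed value and the value used for eligibility are formed from them.
- Reconcile section 5.7 and SOP 9.4 to one centrifugation setting, and state the clotting step in both or refer from one to the other. The documents do not show which setting was intended, so that is for the sponsor and the laboratories to settle.
- Correct SOP 9.7 so that the glucose specimen is named consistently with section 5.5.
- Require the same procedure on day 1 and day 28 for each participant.
- State which text prevails if the protocol body and an SOP differ.

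The cost is edits to the SOPs, forms and data capture screens. Compared with SOP 9.8 read literally, each visit takes about 5 + 2 + 2 = 9 minutes longer plus cuff time, which section 5.5 already requires.
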